This is a Prospective Randomized Controlled trial that will be conducted at the National Cancer Institute. All patients who are eligible for the study will be included and randomized into 3 equal groups.

PATIENTS AND METHODS

After approval from the Ethics Committee at the National Cancer Institute, Cairo University, and obtaining written informed consent, eighty-one patients with thoracic segmental pain due to metastasis, unresponsive to conventional therapy and meeting the inclusion criteria will be randomly assigned to either one of the two types of treatment, PRF or TRF lesioning of the DRG or the control group. Patients will be carefully evaluated for neurologic deficits and side effects. Assessment of pain will be done at baseline then at 1, 3, 6 months after the procedure. Randomization will be done using randomized permuted block design. Randomization list will be generated through random.org online site.

INCLUSION CRITERIA:

1. A greater than 6-month history of segmental pain of thoracic vertebral body metastasis origin.

2. Unsatisfactory pain control with oral pharmacotherapy including strong opioid with VAS >5 .
3. Absence of a chronic or progressive motor deficit.
4. Absence of significant sensory deficit.
5. No indication for percutaneous or open surgical intervention.
6. Magnetic resonance imaging and Computed Tomography evidence of thoracic involvement.
7. ASA status of II to III .
8. Age \geq 18 .
9. Body mass index (BMI) :less than forty and more than twenty .
10. Informed consent

EXCLUSION CRITERIA:

1. Known sensitivity or contraindication to injected materials: local anesthetics.
2. History of psychological disorders.
3. Evidence of significant neurological deficit.
4. Inability to lie prone.
5. Local contraindication to procedure e.g. local sepsis at the site of intervention, coagulopathy.
6. Patient refusal.

Patients will be randomly assigned and divided into 3 equal comparable groups. Before the procedure, laboratory investigations, Dorsal X-ray, CT and MRI will be done. All Patients will be interviewed and examined by physicians trained in interventional pain management. Patients will be carefully assessed on physical exam for sensory, motor, or reflex deficit and

carefully documented. Patients will be informed about the technique of the blocks, and written informed consents will be obtained.

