QOL. The EORTC **QLQ-BM22** is a sub-module of the QLQ-C30 and is an internationally recognized and validated scale used to measure QOL in bone metastases patients ²³. The QLQ-BM22, includes four subscales: painful sites, pain characteristics, functional interference, and psychosocial aspects. Both questionnaires use a 4-point Likert scale ranging from 1 (not at all) to 4 (very much) to rate each item, except for the final 2 question of the QLQ-C30 pertaining to overall QOL which is scored from 1 (very poor) to 7 (excellent). Each subscale is then linearly converted to a score from 0 to 100. For the QLQ-BM22, a higher score indicates worse symptom burden for painful sites and pain characteristics, and better functioning for functional interference and psychosocial aspects. For the QLQ-30, higher scores in the emotional, physical, and QOL scales indicate greater functioning and better ²¹.

VAS, ODI, QLQ-C30 and QLQ-BM22 will be used to evaluate pain, quality of life, and performance status before the procedure and at 3 days and 1, 3, 6 months after the procedure²⁴.

In the holding area, midazolam 0.02 mg/kg IV will be given after fixation of a 20 G cannula. All RF procedures will be performed in the hospital outpatient ambulatory care setting using local anesthesia and conscious sedation as necessary, with fluoroscopic guidance to facilitate needle placement. The segmental spinal levels treated will be selected based on the patients' pain referral pattern as determined by history and physical examination findings. After sterile skin preparation, RF will be performed with the patient in the prone position with mild flexion of the spine and the fluoroscopy beam positioned in an antero-posterior (AP) direction. A 10 cm RF needle 20 G with a 10 mm active tip. The image intensifier will be rotated in a cephalo-caudad direction until the endplates of the adjacent thoracic intervertebral discs is lined up and the transverse processes became discernable from the ribs. The needle is then inserted in a slightly medial-cephalad direction under the transverse processes, and using lateral fluoroscopic imaging, incrementally walking into the thoracic intervertebral foramen . The correct position of the needle's tip should be exactly in line with the facet joint spaces on the anteroposterior projection of the image intensifier, and in the posterior part of the foramen on the lateral projection. Once correct needle position is

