confirmed by image and since neural tissue cannot be seen on plain radiographs and the DRG may vary with respect to its spatial relationship with the intervertebral foramen, so the location of the needle tip will confirmed not only by image but also by sensory stimulation at 50 Hz. The point of maximum stimulation is where sensory response in the painful dermatome can be elicited with stimuli below 0.5 V intensity and this is designated to be the location of the DRG. Slight redirection can be done to optimize the stimulation; injection of contrast reveals epidural uptake. After establishing the site for the RF, 1 ml 2% lidocaine should be injected through the needle. The needle is then connected to a RF generator (Baylis Medical com. Inc. Canada).

Group 1: Patients will receive PRF with temperature 42°C for 480 sec., 2 active cycles per second of 20 milliseconds each , with a voltage output 40 to 60-V range, impedance ranges between 150 and 400 Ohms at all levels using Fluoroscopic guidance (FG). The block will be done as that described by **Young-Chang P. et al** ⁸.

Group 2: Patients will receive TRF with temperature 80°C for 90 sec., 2 cycles, using FG . The block will be done as that described by **Ken-ichiro U** ¹⁶.

Group 3: The control group having identical needle placement and preparation without the RF lesioning (only local anesthetic).

OUTCOME AND ASSESSMENT

Primary outcome measure:

It will include:-

-VAS, ODI, QLQ-C30 and QLQ-BM22 to evaluate pain, quality of life, and performance status at 1, 3, 6 months after the procedure.

Secondary outcome measures:

It will include :-

- Neurological defects .
- Dysthesia and hypoesthesia.
- Change in physical activities, and analgesic use.
- Any other complication from either the technique as pneumothorax or local anesthetic, anesthesia dolorosa and burning pain.
- Patients' satisfaction with analgesia through a phone call a week after procedure on 5-level likert scale, (not satisfied at all, only slightly satisfied, somewhat or partly satisfied, very satisfied, perfectly satisfied)

STATISTICS

1 - Sample size estimation:

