According to studies ^(13,15,16) , to see a significant reduction in VAS defined as at least 50% reduction, ODI, QLQ-C30 and QLQ-BM22 score ($P < 0.01$) with a background standard deviation of 1.0, significance level of 0.05 and power of a test of 80%, minimum number of patients needed would be 25 per group. Because difference in VAS , ODI, QLQ-C30 and QLQ-BM22 score will be more evidenced with control group, the number needed would be much smaller , so the total number needed in the present study would be 69 patients that will be randomized into 3 equal groups. For non-parametric correction, we increased the number to 27 patients for each group.

2- Statistical analysis plan:

Data will be analyzed using SPSS version 18.0. Numerical data will be presented as mean, standard deviation or median and range as appropriate. Categorical data will be presented as numbers and proportions. Mixed models ANOVA will be used to show effect of time on pain score and also to evaluate group interaction. Non-parametric tests ; Friedman's test will be used if data did not show normal distribution. Significance level will be considered at 0.05.

REFERENCES

1. **Smith HS.** and **Barkin RL**, Painful boney metastases, American Journal of Therapeutics , 2014 ;21(2):106-130.
2. **Patrick W.**, Bone Cancer Pain: From Mechanism to Therapy, Current opinion in supportive and palliative care 2014 ; 8(2): 83–90.
4. **Bhatia A.** , Questions Regarding "Pulsed Radiofrequency for Chronic Intractable Lumbosacral Radicular Pain: A Six-Month Cohort Study", Pain Medicine 2016; 17(5):989.
6. **R. Carter W. Jones III**, Neuroinflammatory effects of Radiofrequency, European Journal of Pain 2014; 18 :149-150.
7. **Zeldin A. and Ioscovich A.**, Pulsed Radiofrequency for Metastatic Pain Treatment, Pain Physician 2008; 11:921-922 .

8. **Young-Chang P. Arai, Makoto N., Yoshihiro Y., Maki A., Miki K., Chiharu S., Akiko K., Kazuyo K., and Tatsunori I.,** Dorsal Root Ganglion Pulsed Radiofrequency for the Management of Intractable Vertebral Metastatic Pain: A Case Series, *Pain Medicine* 2015; 16:1007 – 1012.

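### Four unranked primary instruments share one 0.05 level with no success rule, primary arm contrast or multiplicity control, and the only test named for non-normal data cannot compare the arms

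*Combined protocol and SAP*

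**What the plan says.** Under Outcome and Assessment, the primary outcome measure is a single entry: "VAS, ODI, QLQ-C30 and QLQ-BM22 to evaluate pain, quality of life, and performance status at 1, 3, 6 months after the procedure". No instrument is put first. Patients and Methods describes the two QLQ questionnaires by their subscales ("Each subscale is then linearly converted to a score from 0 to 100"), and no subscale is chosen as primary.

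Study Design has three arms: "All patients who are eligible for the study will be included and randomized into 3 equal groups". The title compares thermal with pulsed radiofrequency. The sample size text leans instead on the control arm, saying that the difference in the four instruments' "score will be more evidenced with control group, the number needed would be much smaller".

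The statistical analysis plan says:

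- "Mixed models ANOVA will be used to show effect of time on pain score and also to evaluate group interaction"
- "Friedman's test will be used if data did not show normal distribution"
- "Significance level will be considered at 0.05"

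The sample size paragraph defines an effect for one instrument only: "to see a significant reduction in VAS defined as at least 50% reduction". It also shows P < 0.01 beside the list of four instruments, and then sets the significance level at 0.05 in the same sentence.

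**The concern.** With four primary instruments and three arms, a reader needs to know what result would make the trial positive. The plan gives no rule. If the instruments disagree, or the thermal and pulsed arms each beat control but do not differ from each other, the plan does not say what the trial has concluded. If success may be claimed on whichever instrument reaches significance, the nominal 0.05 does not hold for the main claim.

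The non-normal branch has a second fault, which does not depend on the success rule. Friedman's test asks whether scores change over time within patients. It has no term for treatment arm. If the data are judged non-normal, the plan names no between-arm test for any primary instrument, although the sample was enlarged to 27 per group expressly for non-parametric analysis.

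**Working it through.** **Inputs from the documents.** Four primary instruments; three equal arms of 27; primary visits at 1, 3 and 6 months plus baseline; alpha 0.05; power 80%; SD 1.0; minimum 25 per group. **Assumed, because the documents do not give them:** two-sided tests, correlations between instruments and between visits, and complete normal data.

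**1. The plan's own figure.** The 25 per group cannot be reproduced, because no absolute difference between arms is stated. Solving backwards, √(2/25) × (1.960 + 0.842) = 0.79 SD by the normal formula, or 0.81 SD with the t distribution. I use 0.81 SD below only to price the fix.

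**2. Chance of at least one false positive, one test per instrument.**

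- Independent tests: 1 − 0.95⁴ = 18.5%.
- Equal correlation ρ, two-sided z tests, c = 1.96: 1 − ∫ φ(u) [Φ((c − √ρ u)/√(1−ρ)) − Φ((−c − √ρ u)/√(1−ρ))]⁴ du. This gives 17.4%, 15.6%, 13.0% and 9.4% at ρ = 0.3, 0.5, 0.7 and 0.9.
- Simulated group-by-time tests (3 × 27, baseline plus three visits; visit correlation exchangeable 0.5, or AR(1) 0.5 to 0.9; 20,000 trials per setting):

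| Instrument correlation | 0.3 | 0.5 | 0.7 | 0.9 |
|---|---|---|---|---|
| Greenhouse-Geisser corrected | 16-18% | 15-16% | 13% | 9-10% |
| Uncorrected, exchangeable | 17% | 16% | 14% | 10% |
| Uncorrected, AR(1) | 21-25% | 19-23% | 16-19% | 12-14% |

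If all four must be significant, the rate is 0-2% corrected and at most 3% uncorrected.

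These runs leave out the 3-day assessment, which Patients and Methods schedules but the primary outcome does not list. Adding it takes the worst uncorrected figures to about 28-29% for any one and about 3.5% for all four; the corrected figures barely move.

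**3. Size of a single test.** Uncorrected, the group-by-time test runs at 6.2%, 6.8% and 7.4% under AR(1) 0.5, 0.7 and 0.9. With the Greenhouse-Geisser correction it runs at 4.8-5.1%.

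**4. Friedman's test on all 81 patients.** When all arms improve equally by 0.81 SD, so that the arms do not differ, it rejects in 100% of trials. When the arms change by +0.5, 0 and −0.5 SD, so that they do differ, it rejects in about 4%. It responds to time and not to treatment.

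**5. Power under Holm.** Take 0.81 SD in one arm at all post-procedure visits and exchangeable visit correlation 0.5. The group-by-time F has 6 and 234 degrees of freedom and noncentrality 27 × 0.81² × (3/4) × (2/3) / 0.5 = 17.7. Uncorrected power is about 90% at 0.05 and 77% at 0.05/4 = 0.0125. Patients and Methods lists ten QLQ-C30 scales and four QLQ-BM22 scales; with VAS and ODI that is up to 16 scores, and power at 0.05/16 = 0.0031 is about 61%. With the correction, the first two figures are 89% and 75%.

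**The case against.** The best defence is that VAS is plainly the lead. It has the only defined effect, eligibility is set on it, and the pain score is the only outcome named for analysis. On that view the one test written down carries no fourfold inflation. The signals are real, but none is a declaration: the primary outcome entry and the sample size text both list all four instruments. If only VAS is analysed, three declared primaries have no analysis.

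A second defence is that the sample size sentence joins the instruments with *and*, which may mean that all must improve. That is possible, and it would remove the inflation, but the plan does not state it.

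A third is the P < 0.01. As a per-instrument threshold it would give 1 − 0.99⁴ = 3.9% for four independent tests. It cannot be read as the trial's control, because the same sentence and the analysis plan both set 0.05.

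A reader might also infer more than the documents support:

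- **That the error rate is 18%, or 25% and above.** The first needs the any-one rule and low correlation. The second also needs an uncorrected test and AR(1) visits. The plan states none of these, and a mixed model could use a modelled covariance.
- **That separate visits, subscales or arm pairs multiply the tests further.** They would if each were tested, but the plan does not say that they will be.
- **That the primary outcome was chosen after results were known.** Recruitment ended on 30 July 2018, so six-month visits would end about 30 January 2019, before the document's last update on 31 March 2019. The approvals date from 2016-2017 and the outcome text is undated. The dates make this possible but do not show it.

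**Conclusion.** The concern holds in two parts. First, and certain: the plan has four unranked primary instruments and one 0.05 level, with no success rule, primary arm contrast or multiplicity control. The size of the resulting error is conditional: about 9-18% with valid tests if any one instrument counts, for assumed correlations of 0.9 down to 0.3, and no inflation if all four must succeed. Second, and free of those assumptions: Friedman's test cannot test a difference between arms, so the non-normal branch leaves the trial's question without a test. The normal branch does have one, the group-by-time interaction, so it would be wrong to say that the plan has no between-arm test at all.

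**What to change.** **If no outcome data by arm have been seen:**

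- Name VAS as the single primary outcome; make ODI, QLQ-C30 and QLQ-BM22 secondary.
- Keep the planned group-by-time test on VAS at baseline, 1, 3 and 6 months, at 0.05 with a Greenhouse-Geisser correction. State that the 3-day score is not part of the primary test.
- Test the three arm pairs at 0.05 only if the overall test is significant. With exactly three arms this holds the family-wise error at 5% when the tests are valid (simulated 3.5-4.9% with the correction).
- Replace Friedman's test as the fallback with a between-arm rank-based test, such as rank analysis of covariance on the mean of the 1, 3 and 6 month scores with baseline as covariate.

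A baseline-adjusted comparison at one visit is an acceptable alternative only if the visit is named in advance.

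**If outcome data by arm have been seen:** keep all four instruments, with the same corrected test and the same rank-based fallback. Apply Holm across every primary score actually tested. Test arm pairs only within an instrument whose overall test passes its Holm step, at that step's level. Holm then protects the statement that the arms differ on an instrument, not every pair. Label as post hoc any choice of lead instrument, visit or QLQ subscale.

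**Cost.** No extra patients or visits. On the VAS route, three instruments lose primary status. On the Holm route, under the assumptions of step 5, first-step uncorrected power falls from about 90% to 77% for four tests and to about 61% for 16, and slightly lower with the correction.

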Three prospective controlled trials have examined TRF-DRG for treating neuropathic pain stemming from cervical DRG. Van Kleef et al., 1996, Slappendel et al. , 1997 and Haspeslagh et al. , 2006. **Van Kleef et al.** performed a randomized, sham controlled, double blind study with cervicobrachialgia unresponsive to conventional therapy of 12 months duration and response to diagnostic selective nerve root blocks. In a double-blinded fashion, subjects were randomization to the RF group with conventional lesioning of the DRG at 67⁰C for 60 seconds versus no lesioning in the control group. At 8 weeks post operation, eight out of nine RF patients reported success, while two of 11 in the control group, defined as greater than 2- point reduction on the visual analog scale (VAS). This suggested short-term success where dyesthesia and hypoesthesia side effects were short lived (lasting <3 months).

There have been no prospective controlled trials on TRF of the thoracic DRG. **Stolker et al.** (Stolker et al., 1994) conducted a prospective uncontrolled trial using TRF of the thoracic DRG at 67 °C to treat 45 patients afflicted with thoracic segmental pain. They reported that 91% patients obtained > 50% pain relief at 2 months and that 78% continued to experience pain relief for 13 to 46 months. A smaller number of patients (13.3%) reported a transient burning pain in the corresponding dermatome that subsided within 3 weeks. In Neuropathic Pain their review, Malik and Benzon (Malik & Benzon, 2008) concluded that larger-scale, longer term, controlled clinical trials are required to clearly establish the efficacy of TRF-DRG for different types of neuropathic pain, particularly pain originating from thoracic DRG¹⁶. Although prospective observational and retrospective studies have yielded consistent support for DRG treatment in the cervical, thoracic, lumbar, and sacral regions , controlled studies are less compelling, complicated by the challenge of the lurking deafferentated pain potential. Further, patient selection appears to be vague in predicting treatment outcomes. Larger, sham-controlled, prospective studies are required to elucidate the place of TRF treatment of the DRG for treatment of chronic pain.

AIM OF THE WORK

To evaluate the effectiveness and safety of Pulsed and Thermal Radiofrequency lesion of the dorsal root ganglion (RF-DRG) on a consecutive group of patients presenting with chronic thoracic pain due to vertebral bone metastasis.

STUDY DESIGN

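### Harms are named secondary outcomes but have no collection time or recall window, so transient burning pain after thermal radiofrequency may be missed or under-recorded

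*Combined protocol and SAP*

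**What the plan says.** The stated aim covers safety as well as effectiveness. Under OUTCOME AND ASSESSMENT, the secondary outcomes list neurological defects, "Dysthesia and hypoesthesia", and "Any other complication from either the technique as pneumothorax or local anesthetic, anesthesia dolorosa and burning pain". None has a time point, a method of collection or a grading.

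PATIENTS AND METHODS makes one general commitment: "Patients will be carefully evaluated for neurologic deficits and side effects". It carries no date. The next sentence, "Assessment of pain will be done at baseline then at 1, 3, 6 months after the procedure", concerns pain only.

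Two contacts before 1 month can be found:

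- A later paragraph of PATIENTS AND METHODS, after the description of the QLQ-BM22, places the VAS, ODI, QLQ-C30 and QLQ-BM22 "before the procedure and at 3 days and 1, 3, 6 months after the procedure". The 3-day time is absent from the pain schedule quoted above and from the primary outcome statement.
- The secondary outcomes include "Patients' satisfaction with analgesia through a phone call a week after procedure on 5-level likert scale". No other content is given for this call.

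On the expected course of these events, the Introduction says that after thoracic TRF 13.3% of patients "reported a transient burning pain in the corresponding dermatome that subsided within 3 weeks". It also says that dysesthesia and hypoesthesia after cervical thermal lesioning lasted less than 3 months.

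The Statistical analysis plan says categorical data will be given as numbers and proportions. It does not define the period over which a harm counts.

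**The concern.** A complication proportion needs a period at risk and a way of finding the event. The plan gives neither. This matters most for burning pain, because the trial's own background evidence says that it comes and goes before the first follow-up time on which all the schedule statements agree, which is 1 month. A patient whose burning pain ended in week 2 or 3 could reach the 1-month visit with nothing to report unless asked what had happened since the procedure.

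The early contacts do not clearly close the gap. The 1-week call is a satisfaction rating. The 3-day set, if it takes place, measures pain intensity, disability and quality of life. The VAS there is the average of current, best and worst pain over 24 hours, so as described it cannot separate new burning pain from the metastatic pain under treatment. An early harm could be read as weak efficacy.

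At stake is whether the report can give a usable early incidence of an event that the trial names as an outcome.

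**Working it through.** The plan gives no figure for expected harms, so there is none to reproduce. The check sets the contacts side by side and then sizes the possible loss.

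**Contacts and their stated content**

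| Contact | Where stated | Stated content | Harms stated as asked? |
|---|---|---|---|
| 3 days | PATIENTS AND METHODS, questionnaire paragraph only | VAS, ODI, QLQ-C30, QLQ-BM22 | No |
| 1 week | Secondary outcome measures | Satisfaction, 5 levels | No |
| 1, 3, 6 months | PATIENTS AND METHODS (both schedule statements); primary outcome | Pain and the questionnaires | No |
| Undated | PATIENTS AND METHODS | Evaluation of neurologic deficits and side effects | Yes, no time given |

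No dated contact is said to collect harms. The two that fall inside the cited 3 weeks have other stated purposes.

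**Inputs for scale**

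- Burning pain 13.3%, 45 patients, uncontrolled study of thoracic TRF at 67 °C (Introduction). 0.133 × 45 = 5.985, so 6 of 45.
- 27 patients per arm (Sample size estimation).
- This trial's TRF arm is stated at 80 °C, so carrying the rate over is an assumption.

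**Expected cases in the TRF arm**

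- 27 × 0.133 = 3.6.
- Chance of at least one case: 1 − (1 − 0.133)^27 = 0.979.
- Exact 95% interval for 6/45: 5.1% to 26.8%. 27 × 0.051 = 1.4 and 27 × 0.268 = 7.2.

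**Cases recorded if first asked about at 1 month**

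Let r be the share of resolved cases recovered by recall. Recorded cases = 27 × 0.133 × r.

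- r = 0 (current symptoms only, all resolved by 3 weeks): 0.
- r = 0.5 (assumed): 1.8.
- r = 1: 3.6.

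The documents do not say which of these applies.

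**Would full capture change a significance test?**

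Two-sided Fisher test at 0.05, 27 against 27, taking 0 events in the comparison arm (assumed):

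- 5 against 0: p = 2 × C(27,5)/C(54,5) = 2 × 80,730/3,162,510 = 0.051, not significant.
- 6 against 0: p = 2 × C(27,6)/C(54,6) = 2 × 296,010/25,827,165 = 0.023, significant.
- Power is therefore the chance of 6 or more events among 27 at 13.3%, which is 0.14.
- At a true rate of 27%, near the upper limit of the interval, power is 0.78.

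**The case against.** The strongest reply is that the plan does not say that harms are checked at months 1, 3 and 6, or that only symptoms present on the day are recorded. Those times belong to pain and the questionnaires. The promise to evaluate side effects is undated and could be met by asking at 1 month about everything since the procedure, or through spontaneous reports. This stands. A reader might infer that the trial will under-count TRF harm, or will record none of the burning pain. The documents support only that it may.

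The early period is also not shown to be wholly unobserved. The caption to Fig. 1 mentions a patient diary for the VAS, and the QLQ-BM22 has a pain-characteristics subscale. This stands in part: the diary's frequency is not stated, and neither instrument is described as collecting harms.

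Three further inferences are tempting and are not supported:

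- That the 3-week argument covers all the listed harms. It covers burning pain. Dysesthesia and hypoesthesia, lasting under 3 months, may still be present at 1 month, and no duration is given for neurological defects or pneumothorax.
- That the loss biases the comparison in favour of TRF. This is plausible for an ablative lesion, but the documents give no burning-pain rate for pulsed radiofrequency or for needle placement alone.
- That a finding of no difference in complications would arise only from looking too late. At the cited rate, such a finding is likely even with full capture.

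Finally, the 13.3% comes from one small uncontrolled study at a different temperature. This limits the size estimate but does not remove the gap in the schedule.

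**Conclusion.** The point holds as a gap in the schedule. Harms are named outcomes without a collection time or recall window at any stage of follow-up, and neither early contact is stated to ask about them. Transient burning pain after TRF may therefore be missed or under-recorded if it is first asked about at 1 month.

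The size is up to about 3.6 unrecorded cases among 27 (up to 1.4 to 7.2 over the interval). It depends on the cited rate and the 3-week duration carrying over, and on how well patients recall resolved symptoms. The consequence is chiefly for the descriptive incidence of harm, since about 14% power leaves little for a formal comparison to lose. That last statement also depends on the cited rate: near the top of its interval, missed cases could affect a test as well.

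This should be corrected because the remedy is cheap and changes what is collected.

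**What to change.** - In all three arms, add to the planned 1-week call a fixed yes/no list of the safety outcomes already named, with onset, severity and whether ongoing.
- Reconcile the two schedule statements in PATIENTS AND METHODS and the primary outcome statement on whether the 3-day contact takes place. If it does, use the same list there.
- At 1, 3 and 6 months, record any occurrence since the last contact with start and stop dates, not only status on the day.
- Report per arm the proportion with any event from procedure to 1 month, separately from events persisting at 3 and 6 months.

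The cost is a longer call and one more form page, with no new visit. Reported event rates will be higher, because patients are asked directly.

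The document dates suggest that collection may already be over: recruitment ended on 30 July 2018, six months later is 30 January 2019, and the document was updated on 31 March 2019. In that case, the report should state when and how harms were asked about, and should not present the absence of recorded early events as evidence of safety.

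### The 80% power claim is attached to a 50% VAS reduction that no outcome or analysis uses, and 25 (finally 27) per group does not follow from the stated inputs

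*Combined protocol and SAP*

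**What the plan says.** **Sizing (Statistics, 1 - Sample size estimation).** The target is "a significant reduction in VAS defined as at least 50% reduction". The same sentence covers ODI, QLQ-C30 and QLQ-BM22 and carries a parenthetical P < 0.01. The numerical inputs are "with a background standard deviation of 1.0" and "significance level of 0.05 and power of a test of 80" (percent). The result is "minimum number of patients needed would be 25 per group". The text then says "the total number needed in the present study would be 69 patients", because differences from control should be larger, and ends: "For non-parametric correction, we increased the number to 27 patients for each group". It gives no mean difference, response rate, time point or pair of arms.

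**Outcomes (Outcome and Assessment).** VAS and the three questionnaires at 1, 3 and 6 months are primary. Neither the primary nor the secondary list includes a 50% responder outcome.

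**Analysis (Statistics, 2- Statistical analysis plan).** "Mixed models ANOVA will be used to show effect of time on pain score", and also to examine the interaction with group. Friedman's test is the fallback for non-normal data. Categorical data are to be summarised as counts and proportions. No responder variable and no comparison of proportions between arms is named.

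**Background (Introduction).** Of the uncontrolled thoracic thermal series, the protocol says: "They reported that 91% patients obtained > 50% pain relief at 2 months". The sham-controlled cervical trial is reported as 8 of 9 successes against 2 of 11, where success meant a fall of more than 2 points.

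**The concern.** The 50% reduction is the only numerical definition of a worthwhile effect in the sample-size section, and the trial claims 80% power for it. Nothing in the outcomes or the analysis then estimates it. Two things are at stake.

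- The trial could finish without reporting how many patients in each arm reached a 50% reduction, so its result could not be set beside the thoracic series it cites.
- A reader cannot tell what the 80% refers to. It is tied neither to a stated mean difference nor to stated response rates, so a non-significant comparison could not be interpreted against it.

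**Working it through.** **Inputs from the documents.** SD 1.0 (no unit); alpha 0.05; power 80%; 25 per group, then 69 in total, then 27 per group; entry VAS above 5; cited success rates 91% (thoracic thermal series), 8/9 = 89% and 2/11 = 18% (cervical trial).

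**Assumptions.** Two-sided tests. VAS on a 0-10 scale: the assessment section describes a 100 mm line, but the entry criterion of more than 5 and the SD of 1.0 fit 0-10. All response rates other than the cited ones are assumed.

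**Step 1: the plan's own figure.** For two means, n per group = 2(1.960 + 0.842)² / d² = 15.70 / d², where d is the difference in SDs. The plan gives no d, so 25 cannot be reproduced forwards. Solving backwards:

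- d = 2.802 × √(2/25) = 0.79 by the normal approximation, 0.81 by the t-test. As a check, d = 0.8 gives 15.70 / 0.64 = 24.5, rounded up to 25.
- At alpha 0.01, the P value in the same sentence, 25 per group fits d of about 0.97 to 1.00.

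Neither difference is stated. The later steps do not help: 3 × 25 = 75, not 69; 69 / 3 = 23 per group; 3 × 27 = 81, which agrees with the 81 patients in Patients and Methods.

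**Step 2: 50% read as a mean difference.** Half of the entry threshold is 2.5 points. If that is the between-group difference, d = 2.5 / 1.0 = 2.5 and n = 15.70 / 6.25 = 2.5, so 3 per group by the normal approximation. By the t-test, power is 64% with 3 per group and 84% with 4, so 4 are needed. That is far from 25.

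**Step 3: 50% read as a responder rule, 27 per arm.** Power is the sum over x and y from 0 to 27 of Bin(x; 27, p₁) × Bin(y; 27, p₂), counting tables with p ≤ 0.05.

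| Rates | Source | Chi-square | Fisher exact |
|---|---|---|---|
| 89% vs 18% | cervical trial, different success rule | >99% | >99% |
| 91% vs 18% | thoracic series against cervical control | >99% | >99% |
| 60% vs 20% | assumed | 87% | 80% |
| 60% vs 30% | assumed | 59% | 48% |
| 80% vs 60% | assumed | 38% | 26% |
| 70% vs 50% | assumed | 31% | 23% |

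For a lower-arm rate between 10% and 50%, the smallest whole-point gap that reaches 80% power is 32 to 39 points by chi-square and 37 to 42 by Fisher exact, depending on that rate.

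**Step 4: what 27 per group gives for mean VAS.** d = 2.802 × √(2/27) = 0.76 by the normal approximation, 0.78 by the t-test. This is for one pair of arms at one time point, before dropout or multiplicity. Splitting alpha over three pairs of arms (0.05/3) raises it to 0.91. If only 21 per arm were evaluable (assumed loss of about 20%), it would be 0.87 by the normal approximation at alpha 0.05.

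**The case against.** The best defence is that the plan never sized a responder comparison. An SD, an alpha and a power belong to a comparison of means, and the same sentence applies them to three questionnaires that have no 50% rule. On that reading the 50% describes the size of change sought, and a mixed model of scores is the matching analysis. This stands, and it is why mean VAS should remain the main analysis. It does not rescue the number, because the between-group difference is still missing and 2.5 points with SD 1.0 does not give 25.

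Step 2 can also be challenged. It treats a fall within patients as a difference between groups, and it assumes the scale. That is fair: 4 per group shows that the inputs do not yield 25, and is not a proposed sample size.

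A reader might infer that 27 per arm is too few for the 50% rule at most plausible response rates. The documents do not support that. They assume no rates, and the only ones they cite give over 99% power for thermal treatment against control. Those sources are weak (an uncontrolled series and a 20-patient cervical trial with another success definition), but nothing in the documents replaces them. On a grid of assumed rates (higher arm 40-95%, lower arm 10-50%, steps of 5 points), 57 of 102 pairs reach 80% by the pooled normal approximation. Nor does a gap of 40 points apply as a general threshold: it is near the Fisher exact figure, and the plan names no test for proportions.

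Finally, categorical data are to be presented as proportions, so a responder table is not ruled out. It is simply not planned.

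**Conclusion.** The point holds in two parts that need no assumed response rates. The 50% criterion appears in the sample-size text and in no outcome or analysis. The 25 per group cannot be derived from the stated inputs and fits an unstated difference of about 0.8 SD at two-sided 0.05.

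Whether 27 per arm suffices for a responder comparison depends on the contrast. For thermal treatment against control it is ample if anything like the cited rates applies. For pulsed against thermal, the comparison in the trial's title, both arms are active and a gap above 30 points would need justification; an assumed 50% vs 70% gives 31% power by chi-square and 23% by Fisher exact. The plan states no dropout allowance for its six-month follow-up, and any loss lowers these figures.

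This should be corrected, but it does not invalidate the planned analysis of mean scores.

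**What to change.** 1. Replace the power sentence with what the sample delivers: 27 per group gives 80% power for a mean VAS difference of about 0.78 SD between two arms (two-sided 0.05, before dropout or multiplicity). Name the time point and the pair of arms, and remove the 50% rule from the power claim.
2. Keep mean VAS as the main analysis.
3. Add a supportive analysis: the proportion with at least a 50% VAS reduction from baseline at months 1, 3 and 6, by randomised arm, with risk differences and 95% confidence intervals for each pair of arms.
4. State how deaths and missing values enter that proportion, and add a sensitivity analysis under another rule. Counting them as failures is one defensible choice among several.

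**Cost.** One sentence and one table. VAS is already collected at these visits, so no new data or patients are needed. The intervals for pulsed against thermal treatment will be wide, and power on this outcome is low. Recruitment ended on 30 July 2018 and the document is dated 31 March 2019, so the responder analysis must be labelled post hoc if it is added after the data were seen.
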